9.5.3 Study Halting Rules

Enrollment, dosing and study procedures will be halted for SMC review/recommendation if any of the following are reported:

- Any death occurring after administration of study drug through the subject's last study visit that was not the result of trauma or accident, regardless of relatedness to study product.
- Any subject experiences laryngospasm, bronchospasm, or anaphylaxis within one day after administration of study product.
- Any subject experiences a study drug-related Stevens Johnson Syndrome.
- Two or more subjects experience generalized urticaria within three days after administration of study product.

-
- Any subject experiences a study drug-related SAE from the time of receipt of study drug through the subject's last study visit.
 - Two or more subjects develop new QTc prolongation on EKG that are deemed clinically significant by a reviewing cardiologist.
 - Two or more subjects develop grade 3 laboratory abnormalities deemed related to the study drug.

If any of the halting rules are met following any subject receipt of study drug, the study will not continue with the remaining enrollments without a review by and recommendation from the SMC to proceed.

DMID retains the authority to suspend additional enrollment and study interventions/administration of study product during the entire study, as applicable.

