Subjects will be administered oxfendazole by a study nurse or investigator on days 1, 2, 3, 4 and 5. Subjects will be fasting (water is permitted) for eight hours prior to, and for two hours after, the administration of drug. On the 1st and 5th day of drug administration intensive blood sampling will be performed for PK studies (pre-dose and 30 minutes, 1, 2, 3, 4, 6, 9, and 12 hours following the dose). On days 2, 3 and 4, blood sampling for PK studies will be performed prior to each dose and 2 hours after each dose. On day 6, blood sampling for PK studies will be performed approximately 24 hours following the dose on day 5. Monitoring will start immediately after dosing and will continue for 10 days. Safety laboratories will be performed on days 1, 3, 5, 8 and 10. EKG studies will be performed at screening, two hours after doses on days 1, 3 and 5, and day 8. Subjects will be interviewed to monitor for AEs and SAEs. Blood sampling for PK studies will be performed on days 8 and 10. In addition, prior to study drug administration on days 2-5, if subjects self-report any new signs or symptoms a targeted physical exam may be performed, if indicated, and the new signs or symptoms will be recorded as an AE or SAE as appropriate.

Following blood sampling performed on each day of dosing, subjects will be allowed to return home. Subjects will be counseled to avoid drug, alcohol and tobacco use through the end of the study (Day 10 for groups 1-3 and Day 14 for group 4).

In the food effects evaluation, 12 subjects will be enrolled into the single dose cross over group. Group 4 can be enrolled concurrently with groups 1, 2, and 3. In group 4, half of the subjects will receive a single dose of 3 mg/kg of oxfendazole following an 8 hour fast and the other half will receive a single dose following a high fat meal. Each subject will be followed with safety laboratories, EKGs and PK studies for 7 days at which time they will cross over to receive a single dose of oxfendazole (3mg/kg) following either a high fat meal or following an 8 hour fast.

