5.4 Withdrawal

5.4.1 Reasons for Withdrawal and Discontinuation of Study Product Administration

Subjects may voluntarily withdraw their consent for study participation at any time and for any reason, without penalty.

Any enrolled subject may withdraw or be withdrawn from the study for the following reasons:

- Medical disease or condition, or any new clinical findings for which continued participation, in the opinion of the site principal investigator or appropriate sub-investigator, would compromise the safety of the subject, or would interfere with the subject's successful completion of the study, or would interfere with the evaluation of responses.
- Subject no longer meets eligibility criteria.
- As deemed necessary by the site principal investigator or appropriate sub-investigator for noncompliance or other reasons.
- Subject withdrawal of consent.
- Subject lost to follow-up.
- Termination of the study.
- New information becomes available that makes further participation unsafe.

If a subject withdraws or is withdrawn prior to completion of the study, the reason for this decision must be recorded in the case report forms (CRFs). Refer to Section 7.8 for procedures to be followed if a subject withdraws from the study.

For the multiple ascending dose groups, if the subject develops a study drug related SAE or grade 3 AE or laboratory abnormality during the five days of study drug administration, study drug will be discontinued though the subject will continue with safety monitoring through the completion of the study. If the subject in the food effect study develops a study drug related SAE or grade 3 AE or laboratory abnormality during the seven days following the first dose of the study drug, they will be discontinued from receiving the second dose of study drug, though the subject will continue with safety monitoring through the completion of the study.

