9.5.2 Dose Escalation Halting Criteria

Prior to dose escalation to the next cohort, the Statistical and Data Coordinating Center (SDCC) will notify the study PIs, DMID medical monitor (MM), and DMID Independent Safety Monitor (ISM) whether the below dose escalation criterion were met. Following enrollment and 10 days of safety follow up of the eight subjects in the dose group.

Dose escalation will not proceed if any of the following dose escalation criteria occur:

- any study drug related SAE
- any study drug related grade 3 AE or laboratory abnormality
- any two Grade 2 AE or laboratory abnormalities of the same laboratory parameter

In addition to these criteria, dose escalation may also stop for other reasons per the advice of the SMC, ISM, or DMID Medical Monitor for further evaluation, discussion, and recommendations from the SMC.

If the above dose escalation halting criteria are NOT met, the dose escalation may proceed with agreement of DMID.

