9.5.4 Individual Halting Rules

- Subject experiences laryngospasm, bronchospasm, or anaphylaxis within 24 hours after administration of study product.
- Subject experiences a study drug-related Stevens Johnson Syndrome.
- Subject experience generalized urticaria within 72 hours after administration of study product.
- Subject experiences a study drug-related SAE from the time of receipt of study drug through the subject's last study visit.
- Subject develops new QTc prolongation on EKG that are deemed clinically significant by a reviewing cardiologist.
- Subject develops any grade 3 laboratory abnormalities deemed related to the study drug.
- Subject develops any grade 3 AE deemed related to the study drug.

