9.6 Safety Oversight (ISM plus SMC)

Safety oversight will be under the direction of an SMC. The SMC will have a formal meeting after the third study group has completed the day 10 study visit. The SMC will review available safety data for Groups 1-3, after the third study group has completed the day 10 study visit. This meeting will be scheduled expeditiously.. If halting rules are identified, more frequent

meetings may be held. The SMC will operate under the rules of a DMID-approved charter that will be written at the organizational meeting of the SMC. At this time, each data element that the SMC needs to assess will be clearly defined. The SMC will advise DMID of its findings.

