9.6.2 Safety Monitoring Committee (SMC)

The SMC is an independent group of experts that advises DMID and the study investigators for many Phase 1 and smaller Phase 2 trials. The primary responsibility of the SMC is to monitor subject safety. The SMC is external to DMID, composed of at least three voting members. The SMC will consist of members with appropriate expertise to contribute to the interpretation of the data from this trial. Its activities will be delineated in an SMC charter that will delineate membership, responsibilities, and the scope and frequency of data reviews.

The SMC will operate on a conflict-free basis independently of the study team. DMID and the SMC may convene ad hoc meetings of the SMC according to protocol criteria or if there are concerns that arise during the study. The ISM or principal investigator may request DMID to convene an ad hoc SMC meeting if a safety concern is identified. A computerized system will be used to acquire any data regarding halting criteria throughout the study. If any of the halting rules are met, the study will not proceed with the remaining enrollments without a review by the SMC. After its assessment, the SMC will recommend continuation, modification, or termination of the clinical trial. The SMC will have access to unblinded data during its closed session.

The SMC will review and discuss safety data at the following milestones:

- The SMC will review available safety data for Groups 1-3, after the third study group has completed the day 10 study visit. Ad hoc review: may be in response to an anticipated safety issue such as a dose escalation or study halting rule being met.
- Final review meeting: 6 to 8 months after clinical database lock to review the cumulative unblinded safety data for the study. The data will be provided in a standard summary format. The SMC may be asked to provide recommendations in response to questions posed by DMID.

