11.3.1 Safety Review

The SMC will have a formal meeting after all subjects in groups 1-3 have completed the day 10 study visit. This meeting will be scheduled expeditiously, but this SMC review is not required prior to enrollment into study group 4. This report will summarize adverse events as described in section 11.4.3 below. Additional safety review may occur if halting rules are met.

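### Protocol Section 9.5.3 sets no study-level halt for repeated related Grade 3 clinical AEs, so no mandatory rule acts on such events arising within 18 of the 36 subjects

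*Protocol*

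**What the plan says.** Protocol Section 9.5.3 lists seven events that halt enrollment, dosing and procedures pending SMC review: non-accidental death; airway events or anaphylaxis; related Stevens Johnson Syndrome; generalized urticaria in two subjects; a related SAE; clinically significant new QTc prolongation in two subjects; and "Two or more subjects develop grade 3 laboratory abnormalities deemed related to the study drug". The last is the only Grade 3 limb, and it is limited to laboratory findings.

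The neighbouring rules are wider. Section 5.4.1 stops a subject's dosing "if the subject develops a study drug related SAE or grade 3 AE or laboratory abnormality during the five days of study drug administration". The dose escalation criteria in 9.5.2 include "any study drug related grade 3 AE or laboratory abnormality", and the sentinel criteria in 9.5.1 match. The individual rules in 9.5.4 have a Grade 3 laboratory item and a separate clinical one: "Subject develops any grade 3 AE deemed related to the study drug".

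On oversight, Section 9.6 says "The SMC will review available safety data for Groups 1-3, after the third study group has completed the day 10 study visit". Section 11.3.1 adds that "this SMC review is not required prior to enrollment into study group 4", and Section 4 says "Group 4 can be enrolled concurrently with groups 1, 2, and 3".

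**The concern.** Six of the seven individual rules in 9.5.4 have a study-level counterpart in 9.5.3. The related Grade 3 clinical AE is the one that does not, and the protocol gives no reason, so this looks like an omission. One example is related diarrhoea at the Appendix B Grade 3 threshold (six or more loose stools) that does not become an SAE. Several subjects could have it without meeting any limb of 9.5.3.

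For much of the trial the sentinel and escalation rules act first. They do not act on events among the last six subjects of Group 3, which has no higher dose level to block. Nor do they act in Group 4, which has no sentinels and is not an escalation step. There, a pause while others are still being dosed depends on someone choosing to call one.

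**Working it through.** **The plan's own figure.** The protocol gives no operating characteristic for any halting rule. The nearest figure is Table 5 in Section 11.2, the chance of at least one AE, 1 − (1 − p)^n. At p = 0.20 this gives 1 − 0.8^8 = 0.832 and 1 − 0.8^12 = 0.931, against the stated 0.83 and 0.93. It reproduces.

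**Which subjects are affected.** Each multiple-dose group has 8 subjects, 2 of them sentinels; Group 4 has 12.

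- Sentinels: 9.5.1 acts on a single related Grade 3 AE.
- Group 1 and 2 non-sentinels: a single such event blocks the next dose level under 9.5.2, although only after all eight have finished 10 days.
- Group 3 non-sentinels: 8 − 2 = 6. Their entry is gated, but no later step is blocked by their own events.
- Group 4: 12, with neither rule.

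The set is 6 + 12 = 18 of 36 (50%), for related, non-serious, unlisted Grade 3 clinical AEs only.

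**A range for the event rate.** The documents give no Grade 3 rate, so the rates below are assumptions. In the single-dose study (Section 2.1.2), 7 × 8 = 56 subjects received drug and none of the related AEs was severe. The upper limit of a two-sided 95% interval for 0 of 56 is 1 − 0.025^(1/56) = 0.0638, used here as the top of the range. It describes single doses, not five daily doses or fed dosing.

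**Chance that a two-subject limb is met in the set.** P(X ≥ 2) = 1 − (1 − p)^n − np(1 − p)^(n−1), with subjects independent.

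The six Group 3 non-sentinels are reached only if none of the 16 subjects in Groups 1 and 2 and neither of the 2 Group 3 sentinels has had such an event. The chance of that is g = (1 − p)^18. (This 18 is the gating subjects, not the set above.) If earlier stops are final, the result is

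g × P(X ≥ 2 of 18) + (1 − g) × P(X ≥ 2 of 12).

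| Assumed rate p | g | P(≥2 of 18) | P(≥2 of 12) | Allowing for gating |
|---|---|---|---|---|
| 1% | 0.835 | 0.014 | 0.006 | 0.013 |
| 2% | 0.695 | 0.050 | 0.023 | 0.042 |
| 5% | 0.397 | 0.2265 | 0.118 | 0.161 |
| 6.4% | 0.305 | 0.320 | 0.176 | 0.220 |

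At 5%: 0.397 × 0.2265 + 0.603 × 0.118 = 0.090 + 0.071 = 0.161. Under the current text the corresponding probability is zero at every rate, because the limb does not exist.

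**Cost in pauses, all 36 subjects.** With laboratory and clinical rates both 1% and independent, each limb alone is met with probability P(≥2 of 36) = 0.0503. Two separate limbs give 1 − (1 − 0.0503)² = 0.098. One pooled limb uses a per-subject rate of 1 − 0.99² = 0.0199 and gives 0.16. With the laboratory rate held at 1% and clinical rates of 2%, 5% and 6.4%, two separate limbs give 0.204, 0.566 and 0.694. These figures do not allow for stops that 9.5.1 and 9.5.2 would already have imposed.

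**The case against.** **The gating is real protection.** A reader might infer that these 18 subjects have no sentinel or escalation protection at all. The documents do not support that for the Group 3 six: they are dosed only after 18 multiple-dose subjects without a related Grade 3 AE, under rules that act at one event. For the same reason the ungated figures of 22.65% and 32.0% overstate the effect at 5% and 6.4%. What stands is that nothing mandatory acts on events arising within the six.

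**Section 9.6.2 may already cover it.** It says "If any of the halting rules are met, the study will not proceed with the remaining enrollments without a review by the SMC". If that included the individual rules in 9.5.4, one related Grade 3 AE would be enough. But then so would one case of urticaria, QTc prolongation or Grade 3 laboratory abnormality, and the two-subject thresholds in 9.5.3 would be redundant. That reading is not tenable.

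**The residual class is small.** Section 9.2.1 describes severe events as usually incapacitating, and the SAE definition in 9.2.2 reaches substantial disruption of normal functioning and important medical events. Some related Grade 3 clinical AEs would therefore already halt the study as SAEs. Two thirds of the set (12 of 18) is Group 4, which receives two single 3 mg/kg doses a week apart; the related gastrointestinal events in the earlier study were mild and occurred at 30 or 60 mg/kg. A laboratory limb also fits the main animal target organs, bone marrow and liver. All of this stands and narrows the point.

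**Oversight exists.** The affected subject is stopped, the ISM or PI can request an ad hoc SMC meeting, and DMID can suspend dosing. The scheduled SMC review will see Group 3 events. It would be wrong to infer that such events go unseen. But those powers are discretionary, and the scheduled review follows Group 3 dosing and does not gate Group 4.

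**Conclusion.** The asymmetry in 9.5.3 is real and probably unintended. Among the six Group 3 non-sentinels and 12 Group 4 subjects, repeated related Grade 3 clinical AEs that are neither serious nor listed trigger no mandatory study-level pause. A two-subject limb would be met there with probability about 1.3% to 22% over assumed rates of 1% to 6.4%. The low end is the more plausible for Group 4.

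The figures assume a common rate, independence and final earlier stops; an SMC-approved restart would move them toward the ungated values. They count only events within the 18, and replacements could raise the numbers slightly. They are the chance that a rule is met and should not be read as harm averted: doses already given cannot be recalled, and the six Group 3 non-sentinels need not be staggered. This is a cheap improvement of low severity.

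**What to change.** Add a bullet to 9.5.3, in the form of the existing laboratory limb, that halts the study when two or more subjects in any group have related Grade 3 clinical AEs. Add the same criterion to the computerized halting check described in 9.6.2. A separate bullet produces fewer pauses than pooling with the laboratory limb (about 10% against 16% at 1% rates), but either form closes the gap.

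The cost is an amendment, approved by DMID and submitted to the IRB, and somewhat more SMC pauses: about 5% rising to 10% over 36 subjects at 1% clinical and 1% laboratory rates, before allowing for earlier stops. The increase is large only if related Grade 3 clinical AEs are common, which is when SMC review is wanted. A pause could also interrupt unaffected subjects' five-day courses, or push Group 4 subjects outside the Day 8 (± 1 day) crossover window. That comparison has little to spare: Section 11.2 gives 80% power only for a coefficient of variation below 0.175. The amendment could therefore say how interrupted courses and missed second periods are handled.

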9.5.4 Individual Halting Rules

- Subject experiences laryngospasm, bronchospasm, or anaphylaxis within 24 hours after administration of study product.
- Subject experiences a study drug-related Stevens Johnson Syndrome.
- Subject experience generalized urticaria within 72 hours after administration of study product.
- Subject experiences a study drug-related SAE from the time of receipt of study drug through the subject's last study visit.
- Subject develops new QTc prolongation on EKG that are deemed clinically significant by a reviewing cardiologist.
- Subject develops any grade 3 laboratory abnormalities deemed related to the study drug.
- Subject develops any grade 3 AE deemed related to the study drug.

9.6 Safety Oversight (ISM plus SMC)

Safety oversight will be under the direction of an SMC. The SMC will have a formal meeting after the third study group has completed the day 10 study visit. The SMC will review available safety data for Groups 1-3, after the third study group has completed the day 10 study visit. This meeting will be scheduled expeditiously.. If halting rules are identified, more frequent

meetings may be held. The SMC will operate under the rules of a DMID-approved charter that will be written at the organizational meeting of the SMC. At this time, each data element that the SMC needs to assess will be clearly defined. The SMC will advise DMID of its findings.

9.6.1 Independent Safety Monitor (ISM)

The ISM is a physician with relevant expertise whose primary responsibility is to provide independent safety monitoring in a timely fashion. The ISM will review SAEs and other AEs as needed and provide an independent assessment to DMID. The University of Iowa will have an ISM with experience in infectious diseases or internal medicine.

9.6.2 Safety Monitoring Committee (SMC)

The SMC is an independent group of experts that advises DMID and the study investigators for many Phase 1 and smaller Phase 2 trials. The primary responsibility of the SMC is to monitor subject safety. The SMC is external to DMID, composed of at least three voting members. The SMC will consist of members with appropriate expertise to contribute to the interpretation of the data from this trial. Its activities will be delineated in an SMC charter that will delineate membership, responsibilities, and the scope and frequency of data reviews.

The SMC will operate on a conflict-free basis independently of the study team. DMID and the SMC may convene ad hoc meetings of the SMC according to protocol criteria or if there are concerns that arise during the study. The ISM or principal investigator may request DMID to convene an ad hoc SMC meeting if a safety concern is identified. A computerized system will be used to acquire any data regarding halting criteria throughout the study. If any of the halting rules are met, the study will not proceed with the remaining enrollments without a review by the SMC. After its assessment, the SMC will recommend continuation, modification, or termination of the clinical trial. The SMC will have access to unblinded data during its closed session.

The SMC will review and discuss safety data at the following milestones:

- The SMC will review available safety data for Groups 1-3, after the third study group has completed the day 10 study visit. Ad hoc review: may be in response to an anticipated safety issue such as a dose escalation or study halting rule being met.
- Final review meeting: 6 to 8 months after clinical database lock to review the cumulative unblinded safety data for the study. The data will be provided in a standard summary format. The SMC may be asked to provide recommendations in response to questions posed by DMID.

10 CLINICAL MONITORING

10.1 Site Monitoring Plan

Site monitoring will be conducted to ensure that human subject protection, study procedures, laboratory procedures, study intervention administration, and data collection processes are of high quality and meet sponsor, ICH/GCP guidelines and applicable regulatory requirements, and that the study is conducted in accordance with the protocol and sponsor's standard operating procedures. The DMID or its designee will conduct site-monitoring visits as specified in the monitoring plan.

Monitoring visits will include, but are not limited to, review of regulatory files, accountability records, CRFs, informed consent forms, medical and laboratory reports, and protocol compliance. Study monitors will meet with investigators to discuss any problems and actions to be taken and document visit findings and discussions.

11 STATISTICAL CONSIDERATIONS

This is an open-label Phase I study to assess the safety and pharmacokinetics of oxfendazole in healthy males and nonpregnant females, ages 18-45. The primary objectives are to assess the safety of oxfendazole administered daily for five days and to assess the safety of oxfendazole administered as a single dose with or without food. The secondary objectives are to define the multi-dose kinetics of oxfendazole and to determine the effect of food on the kinetics of oxfendazole.

Primary endpoints:

1. The rate of adverse events (AEs) related to oxfendazole within 10 days of receipt of oxfendazole given for 5 sequential, daily oral doses of either 3, 7.5 or 15 mg/kg
2. The rate of adverse events (AEs) related to oxfendazole within 7 days of receipt of oxfendazole given as a single daily dose either following an 8 hour fast or following a high fat meal.

Secondary endpoints:

1. Plasma C_{max}, T_{max}, AUC, T_{1/2} of oxfendazole at specified time points following each dose of a 5 day daily regimen of either 3, 7.5 or 15 mg/kg
2. Plasma C_{max}, T_{max}, AUC, T_{1/2} of oxfendazole at specified time points following a single dose of oxfendazole administered after an 8 hour fast or after a high fat meal.

